- Thus, patients with subclinical hypercortisolism may benefit from operative intervention to halt or reverse metabolic complications associated with the disease and the risk of malignant progression.
- The optimal management of patients with subclinical hypercortisolism and adrenal incidentalomas is controversial and no large randomized trial has been conducted.
- We hypothesize that operative treatment would reduce the risk of long term complications of subclinical hypercortisolism and malignant progression, and propose a prospective randomized trial comparing nonoperative and operative management of subclinical hypercortisolism in patients with an adrenal neoplasm.

Objectives:**Primary Endpoints:**

- To determine whether unilateral adrenalectomy in patients diagnosed with subclinical hypercortisolism and adrenal neoplasm results in normalization and/or improvement of hypertension as assessed by reduction in pharmacotherapy and/or normalization of blood pressure (systolic pressure ≤ 140 and diastolic pressure ≤ 90), diabetes as assessed by reduction or elimination of pharmacotherapy and/or improvement in A₁C to $< 6.5\%$, osteoporosis by increase in bone formation markers indicative of increased bone formation, hypercholesterolemia as assessed by a reduction or elimination of pharmacotherapy and/or reduction in LDL levels to risk-stratified goal levels as defined by ATP III, and/or overweight or obesity as assessed by a 10 percent reduction in weight at 6 months.

Eligibility:

- An individual with an adrenal neoplasm less than 5 cm in size with biochemically confirmed evidence of hypercortisolism (2 out of 3: dexamethasone suppression test (DST) > 3 mcg/dL, elevated urine free cortisol, and/or morning ACTH < 2.2 pmol/l) without overt clinical signs and symptoms.
- Age greater than or equal to 18 years.
- Adults must be able to understand and sign the informed consent document.

Abbreviated Title: Subclinical Hypercortisolism

Version Date: 12/19/2016

- Patients must have laboratory and physical examination parameters within acceptable limits based on standard clinical practice.

Design:

- Prospective randomized study comparing adrenalectomy versus observation.
- Patients assigned to the operative arm will undergo adrenalectomy and then followed postoperatively for normalization and/or improvement of metabolic complications associated with hypercortisolism and histologic examination of the resected tumor.
- Patients assigned to the non-operative arm will be monitored for possible complications associated with hypercortisolism for six months, at which point they will cross-over to the operative intervention arm.
- Patients with bilateral adrenal neoplasms will have the larger adrenal neoplasm used as the primary lesion responsible for subclinical hypercortisolism.
- Demographic, clinical, laboratory and pathologic data will be collected for each patient participant. Data will be securely stored in a computerized database.
- Patients will have biochemical testing to determine if their adrenal neoplasm is functioning or nonfunctioning.
- Projected accrual will be 15 to 20 patients per year for a total of 5 years. Thus, we anticipate accruing 62 patients on this protocol.

TABLE OF CONTENTS

Précis	3
Table of Contents	5
1. INTRODUCTION	8
1.1 Study Objectives	8
1.1.1 Primary Objective	8
1.1.2 Secondary Objectives:	8
1.2 Background and Rationale	8
2 ELIGIBILITY ASSESSMENT AND ENROLLMENT	15
2.1 Eligibility Criteria	15
2.1.1 Inclusion Criteria	15
2.1.2 Exclusion Criteria	16
2.1.3 Recruitment Strategies	16
2.2 Screening Evaluation	16
2.2.1 Detailed History and Physical Examination	16
2.2.2 Radiology and Nuclear Medicine Tests	16
2.2.3 Laboratory evaluation	16
2.2.4 Biochemical testing	17
2.3 Registration Procedures	17
2.4 Randomization (or Stratification) Procedures	17
2.5 Baseline Evaluation	18
2.5.1 Detailed History and Physical Examination	18
2.5.2 Quality of Life Questionnaire (see Appendix A)	18
2.5.3 Radiology and Nuclear Medicine Tests	18
2.5.4 Specialty Consults as Required by Patient’s Medical History and Presentation	18
2.5.5 Laboratory evaluation	18
2.5.6 Biochemical testing	19
2.5.7 Other Laboratory Evaluations	19
3 STUDY IMPLEMENTATION	20
3.1 Study Design	20
3.2 Questionnaires	21
3.3 Study Calendar	22

*Abbreviated Title: Subclinical Hypercortisolism**Version Date: 12/19/2016*

3.3.1	Operative Arm	22
3.3.2	Non-Operative Arm	23
3.4	Surgical Guidelines	25
3.5	Criteria for Removal from Protocol Therapy and Off Study Criteria	25
3.5.1	Criteria for removal from protocol therapy	25
3.5.2	Off-Study Criteria	25
3.5.3	Off-Study Procedure	25
4	BIOSPECIMEN COLLECTION	26
4.1	Correlative Studies for Research	26
4.2	Sample Storage, Tracking and Disposition	26
5	DATA COLLECTION AND EVALUATION	26
5.1	Data Collection	26
5.2	ROUTINE DATA COLLECTION	27
5.3	HUMAN DATA SHARING PLANS	27
5.3.1	Human Data Sharing Plan	27
5.4	Response Criteria	27
5.4.1	Definitions	27

1. INTRODUCTION

1.1 STUDY OBJECTIVES

1.1.1 Primary Objective

- To determine whether unilateral adrenalectomy in patients diagnosed with subclinical hypercortisolism and an adrenal neoplasm results in normalization and/or improvement of hypertension as assessed by reduction in pharmacotherapy and/or normalization of blood pressure (systolic pressure ≤ 140 and diastolic pressure ≤ 90), diabetes as assessed by reduction or elimination of pharmacotherapy and/or improvement in A₁C to $< 6.5\%$, osteoporosis by increase in bone formation markers indicative of increased bone formation, hypercholesterolemia as assessed by a reduction or elimination of pharmacotherapy and/or reduction in LDL levels to risk-stratified goal levels as defined by ATP III, and/or overweight or obesity as assessed by a 10 percent reduction in weight at 6 months.

1.1.2 Secondary Objectives:

- To determine the risk of primary adrenal malignancy in patients with subclinical hypercortisolism and adrenal mass less than 5 cm.
- To determine whether FDG PET/CT scan is diagnostic of subclinical hypercortisolism.
- To determine the optimal diagnostic test for subclinical hypercortisolism.
- To determine whether patients show an improvement in quality of life after adrenalectomy compared to medical therapy.
- To determine whether patients have an increased risk of deep venous thrombosis with subclinical hypercortisolism, regardless of treatment.
- To determine whether dermal thickness is diagnostic of subclinical hypercortisolism.
- To determine whether ultrasound of the skin is diagnostic and is able to show resolution of subclinical hypercortisolism after adrenalectomy.

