Since there are no overt clinical signs of cortisol excess and many of the metabolic complications are concomitantly prevalent in the elderly, an interesting study by Morelli, et. al. attempted to address diagnosis of subclinical hypercortisolism by correlating between biochemical diagnostic criteria and clinical metabolic manifestations. Biochemical data from 231 patients with unilateral adrenal incidentalomas was evaluated. The different criteria consisted of various combinations of 1-mg dexamethasone suppression test with varying cut-offs, elevated urinary fractionated cortisol and low basal ACTH. The metabolic complications evaluated included hypertension, type 2 diabetes, and vertebral fractures. The study showed having 2 out of 3 positive results from a combination of a DST cut-off value of >82.8 nmol/l (~ 3 $\mu\text{g/dL}$), elevated urinary free cortisol, and low morning ACTH (<2.2 pmol/l) to have a sensitivity of 61.9% and a specificity of 77.1% of predicting the concomitant presence of all three metabolic complications ($p=0.001$) (24). Given the current level of clinical evidence, we will use a 1-mg dexamethasone suppression test (DST) with a cut-off of 3 $\mu\text{g/dL}$ for screening and either urine free cortisol or low morning ACTH (<2.2 pmol/l) as confirmatory of subclinical hypercortisolism in this study. We will also evaluate other laboratory tests in the diagnosis of subclinical hypercortisolism.

Although there is retrospective data indicating operative treatment as beneficial, the optimal therapeutic paradigm has yet to be defined with quality evidence (1, 3). Retrospective analyses of patients who undergo adrenalectomy has been shown to be beneficial for patients with

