2 ELIGIBILITY ASSESSMENT AND ENROLLMENT

2.1 ELIGIBILITY CRITERIA

2.1.1 Inclusion Criteria

- 2.1.1.1 An individual with an adrenal neoplasm less than 5 cm in size with biochemically confirmed evidence of hypercortisolism (2 out of 3: DST >3 mcg/dL, elevated urine

Abbreviated Title: Subclinical Hypercortisolism**Version Date: 12/19/2016**

free cortisol, and/or morning ACTH <2.2 pmol/l) without overt clinical signs and symptoms.

- 2.1.1.2 Age greater than or equal to 18 years.
 - 2.1.1.3 Adults must be able to understand and sign the informed consent document.
 - 2.1.1.4 Patients must have laboratory and physical examination parameters within acceptable limits by standard of practice guidelines prior to surgery as assessed by preoperative anesthesia assessment.
- 2.1.2 Exclusion Criteria
- 2.1.2.1 Biochemically and/or radiologically confirmed pheochromocytoma, hyperaldosteronoma, or adrenocortical carcinoma.
 - 2.1.2.2 Nonfunctioning adrenal neoplasm.
 - 2.1.2.3 Pre-existing cancers and/or metastatic disease to the adrenal glands.
 - 2.1.2.4 Pregnancy and/or lactation.
 - 2.1.2.5 Lack of metabolic complications.
 - 2.1.2.6 Imaging features worrisome for malignancy (heterogeneous tumor, presence of calcifications, necrosis, >10 Hounsfield units on an unenhanced CT scan, and delayed washout of contrast).

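### Four secondary objectives ask whether a test is diagnostic or optimal, but every enrolled patient is a case under the entry rule and no disease-negative comparator, reference standard or diagnostic analysis is named

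*Combined protocol and SAP*

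**What the plan says.** Section 1.1.2 lists seven secondary objectives. Four concern diagnosis:

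- For the scan, the aim reads "To determine whether FDG PET/CT scan is diagnostic of subclinical hypercortisolism".
- For the choice among tests, it reads "To determine the optimal diagnostic test for subclinical hypercortisolism".
- For the biopsy measure, it reads "To determine whether dermal thickness is diagnostic of subclinical hypercortisolism".
- For the imaging of the skin, which has two parts, it reads "To determine whether ultrasound of the skin is diagnostic and is able to show resolution of subclinical hypercortisolism after adrenalectomy".

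Section 1.2 adds: "We will also evaluate other laboratory tests in the diagnosis of subclinical hypercortisolism". It also calls these questions correlative studies, while still describing them as diagnostic or optimal.

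Section 2.1.1 admits patients "with biochemically confirmed evidence of hypercortisolism (2 out of 3: DST >3 mcg/dL, elevated urine". The quote breaks off within the second of the three criteria; the third is a low ACTH in the morning. Section 2.1.2 excludes "Nonfunctioning adrenal neoplasm". The Précis states "Patients will have biochemical testing to determine if their adrenal neoplasm is functioning or nonfunctioning", but under Section 2.1.2 the nonfunctioning cases do not stay in the study.

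PET/CT and skin ultrasound belong to the baseline evaluation after enrollment (Section 2.5). Section 1.2 takes the skin biopsy for dermal thickness from the operative incision. Section 8.5.1 describes the PET/CT radiation as being for research only.

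Section 7 covers the primary Fisher comparison and Wilcoxon tests of blood pressure and other continuous measures. It gives no method for any diagnostic objective.

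**The concern.** To call a test diagnostic, one must know how it behaves in people without the condition as well as in those with it. Specificity, AUC and any ranking of tests need both groups. The plan enrolls one group only and does not say where the other would come from.

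At stake is what the trial may conclude. A high proportion positive among patients already classed as diseased could be reported as evidence that a scan or hormone test is diagnostic, when the same proportion might be seen in nonfunctioning masses. For PET/CT, participants also receive a research-only exposure for a question that the enrolled cohort alone cannot answer.

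**Working it through.** **Inputs.** Evaluable target 62 (31 per arm) and ceiling 66 (Section 7). Entry rule and exclusion (Sections 2.1.1, 2.1.2). Timing of tests (Sections 2.5, 3.3.1, 3.3.2). Source of the biopsy (Section 1.2).

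**The plan's own figure.** Section 7 states 80% power for 35% against 5% with 31 per arm, two-sided Fisher's exact test at 0.05. Exact enumeration gives 80.9% (30 per arm gives 78.8%). The figure reproduces. It concerns the primary endpoint only; no figure is given for a diagnostic objective.

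**Specificity and AUC at baseline, with the entry rule as reference standard.**
- Disease-negative patients: 0 of 62, or 0 of 66.
- Specificity = true negatives / all negatives = 0/0, not estimable.
- AUC uses positive-negative pairs: 62 × 0 = 0 pairs, not estimable.

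**What can be estimated.** A proportion positive in 62, where a cut-off is fixed. Exact (Clopper-Pearson) 95% limits:
- 31/62 = 50.0%: 37.0% to 63.0%
- 39/62 = 62.9%: 49.7% to 74.8%
- Largest distance from estimate to limit over all possible counts: 13.2 points

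**Selection on the entry tests.** Each patient has at least 2 positives among DST, urinary free cortisol and ACTH. If all three are recorded, at least 62 × 2 = 124 of 62 × 3 = 186 qualifying results are positive (66.7%), so the three sensitivities must sum to at least 2. This floor applies to the qualifying results. The baseline repeats in Section 2.5.6 come from a selected group but are not fixed by the rule. Midnight cortisol, DHEAS and 17-ketosteroids have no such floor, and still no specificity.

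**What the study calendars add.**

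| Test | Operative arm | Non-operative arm | Contrast available |
|---|---|---|---|
| FDG PET/CT | Baseline only | Baseline only | None |
| Dermal thickness | Incision biopsy | Incision biopsy at crossover surgery | None described |
| DST, urinary free cortisol, ACTH, midnight and serum cortisol | Baseline; M3 after surgery | Baseline, M3, M6 before surgery; M9 after | Before/after; M3 between arms |
| Skin ultrasound | Baseline; every follow-up visit | Baseline; every visit before and after surgery | Before/after; M3 between arms |

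The M3 contrast sets up to 31 operated against up to 31 unoperated patients, fewer if any cross over early for overt signs or tumor growth. It is randomized, but it contrasts patients after removal of the gland with untreated patients. It does not contrast patients with people whose mass never secreted cortisol.

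**The case against.** **Post-operative data.** A reader might infer that the plan can report nothing beyond how often each test is positive in diseased patients. The calendars do not support that. Hormone tests and skin ultrasound are repeated after surgery, giving a within-patient contrast and a randomized M3 contrast. This objection stands for those tests, although the plan does not assign the data this role and treated patients are imperfect negatives. It does not reach PET/CT or dermal thickness.

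**Choice of reference standard.** A reader might also infer that specificity is impossible under any standard, or that predictive values are fixed at 100% and 0%. Both follow only if the entry rule is the reference standard, which no section states. Judged against response to adrenalectomy, the cohort would contain both outcomes: at the planned 35%, about 0.35 × 31 = 11 responders in the operative arm. That would make accuracy estimable, but for predicting benefit rather than for diagnosing the condition, and the plan does not specify it.

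**Possible comparators elsewhere.**
- Screen failures would have the screening hormone results, but no section designates them. They would lack protocol PET/CT, skin ultrasound and the biopsy.
- The nonfunctional tumors from protocol 11-C-0149 (Section 1.2, Appendix B) appear as background, set against Cushing's syndrome.
- Section 4.1 sends biospecimens to protocol 09-C-0242, which is not available here. Comparison skin might exist there, but this protocol names none.

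**Status of the objectives.** They are secondary, are described as correlative, and carry no alpha or power. That limits the importance of the gap. It does not make the wording answerable.

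**Conclusion.** The point holds. No disease-negative comparator, reference standard or diagnostic analysis is designated for four of the seven secondary objectives. Taking the entry rule as reference standard (an assumption), there are 0 negatives among 62 or 66 patients, and baseline specificity and AUC are not estimable.

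The force differs by test:
- **PET/CT and dermal thickness:** full. The enrolled cohort alone cannot show that either is diagnostic.
- **Hormone tests and skin ultrasound:** partial. Scheduled repeats can show response to adrenalectomy. They cannot show discrimination from a nonfunctioning mass. The resolution half of the ultrasound objective can be answered.
- **DST, urinary free cortisol and ACTH:** sensitivity is also inflated by selection and incorporation, so ranking tests on it would favor the entry tests.

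The primary endpoint, its power and the sample size are unaffected. The change should be made, but it does not threaten the main result. The conclusion does not depend on the size of the earlier PET/CT dataset, which the text does not state.

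**What to change.** 1. In Section 1.1.2, restate the four objectives as exploratory. For PET/CT and the non-entry hormone tests, report the proportion positive with an exact 95% interval where a cut-off is fixed in advance. For dermal thickness and skin ultrasound, report the distribution. Make no claim from the enrolled cohort alone that a test is diagnostic or optimal.
2. In Section 7, add the before/after and M3 between-arm comparisons for the hormone tests and skin ultrasound, labelled as response to surgery. For the entry tests, give more weight to the randomized M3 contrast, because values selected for being abnormal tend to move back toward normal on repeat.
3. State that DST, urinary free cortisol and ACTH are subject to selection and incorporation bias. Do not rank them against each other or against non-entry tests on sensitivity in this cohort.
4. Claim PET/CT specificity only if the 11-C-0149 nonfunctioning tumors are prespecified as an external comparator, with their number, an exact interval, and a statement that the earlier functional cases had Cushing's syndrome.

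Cost: rewording of four objectives and one analysis paragraph, with no new visits or tests. Item 4 needs access to scan data from another protocol. The downside is narrower claims and a little more analysis.

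As a separate point, Section 1.2 describes the case definition as DST plus one confirmatory test, while Section 2.1.1 accepts any two of three. The two passages must be reconciled.
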